be assessed for symptoms of UTI since surgery by assessment of: urethral discomfort, suprapubic tenderness or pelvic pain, sense of urinary urgency, frequency or dysuria, fever, antibiotic use, and clinical and laboratory data suggesting infection (UA with +leukocyte esterase +/- nitrates, urine culture with $>10^5$ bacterial colony forming units per mL (CFU)). Asymptomatic bacteriuria will be considered a UTI for this study (defined as $>10^5$ CFU/mL on urine culture). Patients who are treated with antibiotics for UTI without laboratory data suggesting infection will be included in UTI group. For participants reporting ED visits prior to 14 +/- 2 day visit, ED reports will be obtained and an assessment will be made regarding the symptomatic UTI diagnosis. Those meeting these criteria will be followed with symptom and laboratory analysis. All positive UA test will be confirmed by laboratory analysis for final diagnosis. Results of +leukocyte esterase +/- nitrites will be considered abnormal. If a diagnosis of UTI does not exist in the patient chart outside of study, the patient's clinical picture will be evaluated independently by 2 separate care providers to determine if meeting criteria for UTI (symptomatic bacteriuria as defined above). If there is discrepancy a third provider will be the determining opinion. Participants meeting the primary endpoint (UTI) will be discontinued from the study following.

Secondary outcomes include: hospital length of stay, readmissions, antibiotic use at the time of surgery and post-surgery. Measures of UTI, and secondary outcomes will be collected from observation during study visits and from the patient medical charts., If closed drainage system was disrupted during placement (to back fill bladder intra-operatively), and method of catheter discontinuation ("fill and pull" versus "pull and void" methods) will be collected for comparison between the groups for analysis as a possible confounding variables.

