Participants will conduct the following study visits over 2 weeks. All costs associated with routine standard of care procedures for catheter insertions and diagnosing and treatment of a UTI will be the responsibility of the patient and/or their insurance provider. All costs associated with procedures conducted for research only will be paid for by the research study.

- **Visit 1 Screening and Enrollment:** Potential participants will be screened and consented for study up to 30 days prior to their surgical procedure. Inclusion/Exclusion criteria will be reviewed at the time of consent and baseline data including physical exam, health history, clinical diagnosis and concomitant medications will be collected following consent. A urine sample will be collected and analyzed 0-24 hours prior to procedure.
- **Visit 2 Randomization and Catheter Insertion:** Participants will be randomized to either the SOC catheter protocol or catheter insertion including Betadine on the day of procedure. Standard protocol will be followed for catheter preparation and insertion. Any adverse events following insertion will be recorded. Pre-operative antibiotics will also be recorded.
- **Visit 3, 24-hour post-op:** Patients will be assessed at 24 hours post-op in-patient. A urine sample will be collected and analyzed. Any positive urine analysis will be further analyzed and confirmed by the UCH laboratory per SOC procedures. Patients will be assessed for symptomatic signs of UTI and review of AEs following procedure.

- **Visit 4; 2-week post op:** Patients will be assessed 2-weeks post-op at their SOC post-op clinic visit. A urine sample will be collected and analyzed. Any positive urine analysis will be further analyzed and confirmed by the UCH laboratory per SOC procedures. A physical exam will also be collected. Patients will be assessed for symptomatic signs of UTI and review of AEs and ED visits since the last visit. Data including hospital stay, readmission, and antibiotic use will be collected. Patient satisfaction with catheter procedure will also be collected. Patient will be finished with study following visit 4.

e. Description, risks, and justification of procedures and data collection tools:

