- Consent and randomization: Patients will be randomized to standard of care intraoperative catheter placement versus aseptic protocol for catheter insertion upon providing informed consent. Randomization will be performed using the REDCap randomization module and will be performed by the study coordinator or research manager.
- Urine analysis with urine dip: Patients will be asked to provide a clean catch urine sample in provided collection cup prior to surgery (done as standard of care), a catheter collected urine sample at 24hrs post-operatively (research procedure) and another clean catch specimen at their 2-week surgical follow-up (research procedure). This collection and analysis is low risk except for the possibility of unnecessary treatment if abnormal sample is obtained. Abnormal samples will be correlated with patient history/complaints and confirmed with formal urine analysis. Confirmation of UTI would also utilize urine culture. The urine analysis by dip gives a fast yet reliable indicator of urinary tract infections. Pre-operative/pre-randomization allows us to exclude patients who may have underlying UTI prior to initiation of the study.
- Catheter placement: The aseptic protocol involves dipping standard catheter in an aseptic betadine solution and leaving a pre-existing plastic cover in place over the catheter during insertion and while in place. We do not anticipate any added risk of the aseptic protocol to the patient although patients may experience some increased irritation due to the protective plastic cover.

Anticipated Risks

While the study anticipates minimal risks, the following outlines any potential minimum risk to subjects:

- i. **Breach of Confidentiality:** Data obtained using information from medical records poses minimal risk. All procedures in which information is being obtained will be conducted per standard of care. There is a risk that a patient's privacy may not be protected. This risk is uncommon.

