- Information that indicates a change to the risks or potential benefits of the research

Adverse events that are deemed not related will be documented in the study AE log, subject study charts, and reported to COMIRB at the time of annual review, per their policy. The PI will review AEs on an ongoing basis.

Anticipated clinical adverse events associated with urine catheter is: urethral/bladder irritation requiring removal of catheter prematurely, bladder or urethral injuries related to catheter placement, folliculitis of the genital area, change in urine color and UTI infection. Symptoms of a UTI are anticipated and include: fever, chills, urethral discomfort, incontinence, dark urine, urinary pain, suprapubic tenderness or pelvic pain, urinary urgency, frequency or dysuria, antibiotic use, prolonged hospital stay or readmission following symptoms. Severe UTIs may result in spread to the kidneys and present with abnormal kidney function assessment.

Anticipated clinical adverse events associated with the use of Betadine are as follows:

- **Common:** skin irritation (burning, redness, or general irritation)
- **Rare but Severe:** severe allergic reaction including rash, gives, itching, difficult breathing, tightness of the chest, swelling of the face, lips or tongue.
- **Unlikely:** balance/hearing problems, hair bumps (folliculitis), change in the amount of urine

There are no known contraindicated medications associated with the use of Betadine.

Serious Adverse Event

A Serious Adverse Event (SAE) is any untoward medical occurrence at any dose that:

- Results in death
- Is life-threatening (defined as an event in which the subject was at risk of death at the time of the event; it does not refer to an event which hypothetically might have caused death if it were more severe)

- Requires inpatient hospitalization or causes prolongation of existing hospitalization (see *NOTE**: below for exceptions)
 - Results in persistent or significant disability/incapacity
 - Is a congenital anomaly/birth defect
- Is an important medical event, defined as a medical event that may not be immediately life-threatening or result in death or hospitalization but, based on appropriate medical and scientific judgment, may jeopardize the subject or may require intervention (e.g., medical, surgical) to prevent one of the other serious outcomes listed above.
- Suspected transmission of an infectious agent (e.g., pathogenic or non-pathogenic) via the study treatment is an SAE.

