
**NOTE: The following hospitalizations are not considered SAEs:*

- A visit to the emergency room or other hospital department lasting less than 24 hours that does not result in admission (unless considered an “important medical event” or a life-threatening event)
- Elective surgery planned before signing consent
- Admissions as per protocol for a planned medical/surgical procedure
- Routine health assessment requiring admission for baseline/trending of health status (e.g., routine colonoscopy)
- Medical/surgical admission other than remedying ill health state that was planned before study entry. Appropriate documentation is required in these cases
- Admission encountered for another life circumstance that carries no bearing on health status and requires no medical/surgical intervention (eg, lack of housing, economic inadequacy, caregiver respite, family circumstances, administrative reason)
- Admission for treatment of suspected/confirmed UTI as this is an anticipated risk and the primary outcome

Participants experiencing a SAE should be discontinued from the study and followed per clinical standard of care. SAEs should be documented on the AE CRF and reported to the IRB within 48 hours of notification of event.

There are no known reports of serious adverse events following standard practice of urine catheter insertion or associated with the use of Betadine.

Data Collection and Confidentiality

This study will obtain approval for conduct through the Colorado Multiple Institutional Review Board (COMIRB) for research involving human subjects. All patients within the Gynecologic Oncology clinic at the University of Colorado Cancer Center who meet the study criteria will be considered eligible for the study. We will not include any vulnerable populations as defined by ethical guidelines. Potential participants will be screened by the PI/Co-I and the research team and approached for consent. Consent will occur prior to the initiation of any study procedures at a scheduled clinic visit in the Gynecologic Oncology clinics of participating sites. Potential participants will be provided a private setting for in-person consent and will be adequately informed of the study intent, requirements, and potential risks and benefits. Patients will also be informed that any participation is voluntary and will not affect any clinical care they are to receive. Research

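### Patients are discontinued after a UTI or an SAE and nothing says outcome collection continues, so satisfaction is missing according to outcome and late asymptomatic bacteriuria can go undetected

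*Combined protocol and SAP*

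**What the plan says.** Two rules take patients out of the study early. Section IV.a (Performance Measurement): "Participants meeting the primary endpoint (UTI) will be discontinued from the study following". The sentence stops there and does not say following what. The Serious Adverse Event section: "Participants experiencing a SAE should be discontinued from the study and followed per clinical standard of care". An SAE includes an event that "Requires inpatient hospitalization or causes prolongation of existing hospitalization". The exceptions to that definition include "Admission for treatment of suspected/confirmed UTI as this is an anticipated risk and the primary outcome".

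Section IV.d (Study Procedures) describes Visit 4, two weeks after surgery, for patients in general and gives no exemption. At that visit "Patient satisfaction with catheter procedure will also be collected", and then "Patient will be finished with study following visit 4". No other time for the questionnaire is given. Section VI compares the responses between arms with a Mann-Whitney-Wilcoxon test.

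On the primary outcome, section IV.a sets a window of 14 +/- 2 days and adds "Asymptomatic bacteriuria will be considered a UTI for this study". Section IV.e lists the 2-week urine sample as "another clean catch specimen at their 2-week surgical follow-up (research procedure". Section IV.a also names medical charts as a source for UTI and secondary outcomes, and section IV.c provides for pulling data by record number. Section VI promises an intent-to-treat analysis and tests UTI at both 24 hours and day 14. Beyond summarising missing data, it gives no rule for a missing outcome.

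**The concern.** Leaving the study and ceasing to supply outcome data are different things, and the plan does not separate them. Read literally, two kinds of data are exposed.

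- **Satisfaction.** Whether a patient answers the questionnaire depends on whether she had an early UTI. That is the outcome the intervention is meant to change, so the two sets of responders are no longer the randomised groups. The chart cannot supply the missing answers.
- **UTI after a non-UTI SAE.** Because admission for UTI is not an SAE, the SAE rule mainly removes patients whose UTI status is still open. They return to standard care, and the 2-week urine sample is not part of that care. Bacteriuria without symptoms is found only if urine is tested.

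A smaller related gap concerns a patient discontinued after a 24-hour UTI. Section VI does not say how she counts in the day-14 test.

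**Working it through.** **Inputs.** From section IV.b: 40% UTI in control, a 50% reduction (so 20% in the intervention arm), 100 per arm, alpha 0.05, power 0.84. The documents do not give the share f of UTIs established before Visit 4, or the SAE rate. Both are assumed below and shown as ranges.

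**The plan's own figure.** Two-sided normal approximation with pooled variance and continuity correction:

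power = Φ{[0.20 − 1/n − 1.96·√(2·0.30·0.70/n)] / √[(0.40·0.60 + 0.20·0.80)/n]}.

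At n = 100 this is Φ[(0.190 − 0.127)/0.0632] = 0.840. The stated 0.84 is reproduced, with no allowance for missing outcomes.

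**Satisfaction.** Expected missing records per 100 are 40f (control) and 20f (intervention). The UTI share among responders is 0.40(1 − f)/(1 − 0.40f) and 0.20(1 − f)/(1 − 0.20f).

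| f (assumed) | Missing, control vs intervention | UTI share among responders | Gap (points) |
|---|---|---|---|
| 0 | 0 vs 0 | 40% vs 20% | 20 |
| 0.25 | 10 vs 5 | 30/90 = 33.3% vs 15/95 = 15.8% | 17.5 |
| 0.50 | 20 vs 10 | 20/80 = 25.0% vs 10/90 = 11.1% | 13.9 |
| 0.75 | 30 vs 15 | 10/70 = 14.3% vs 5/85 = 5.9% | 8.4 |

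A UTI first found at Visit 4 costs no questionnaire, so f = 1 (40 vs 20 missing) is the ceiling.

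**Direction of the satisfaction bias.** Suppose the arms differ in satisfaction only through UTI. Let t_E be the probability that a non-UTI patient rates higher than an early-UTI patient, plus half the ties, minus 0.5. Let t_L = k·t_E be the same quantity for late-UTI patients. The Mann-Whitney effect is 0.20·f·t_E + 0.20(1 − f)·t_L with everyone included, and gap(f)·t_L with early-UTI patients missing. The ratio of the second to the first is k·gap(f)/{0.20[f + k(1 − f)]}. At f = 0.50:

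- k = 0.5: 0.0694/0.150 = 0.46, so the effect is 54% too small.
- k = 1: 0.1389/0.200 = 0.69, so it is 31% too small.
- k = 2: 0.2778/0.300 = 0.93, so it is 7% too small.
- k = 3: 0.4167/0.400 = 1.04, so it is 4% too large.

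The documents give neither f nor k, so the sign is not fixed.

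**Primary outcome after a non-UTI SAE.** Let m patients per 100 in each arm have a wholly unknown outcome (assumption), with 40% and 20% among the rest. The lowest possible difference codes every unknown as UTI in the intervention arm and as no UTI in control. The highest does the reverse.

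- m = 5: known events 0.40·95 = 38 and 0.20·95 = 19. Low 38 − (19 + 5) = 14; high (38 + 5) − 19 = 24 points.
- m = 10: known events 36 and 18. Low 36 − 28 = 8; high 46 − 18 = 28 points.

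If unknowns were simply treated as no UTI, the difference would be 38 − 19 = 19 or 36 − 18 = 18 points. Power on the known outcomes alone, by the formula above at alpha 0.05, is 0.819 at n = 95 and 0.795 at n = 90, against 0.840.

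The outer limits are remote. If unknown patients had the planned rates independently, the low end at m = 5 would have probability 0.20⁵ × 0.60⁵, or about 0.000025.

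**The case against.** The best defence is that the gap is one of wording. Visit 4 is a general schedule, and an early-exit rule elsewhere is an ordinary exception to it. The UTI sentence does not say when discontinuation takes effect. Section IV.a says that patients meeting the criteria on an ED report are followed with symptom and laboratory assessment, and section VI promises intent-to-treat. It is fair to call this an ambiguity rather than a flat contradiction. Even so, none of these passages secures a questionnaire or a urine sample after discontinuation, and the SAE sentence has no missing object.

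The chart defence also stands in part. A symptomatic or treated UTI after an SAE may appear in the chart, and a patient whose SAE came after Visit 3 should already have a 24-hour result. What remains exposed is mainly late asymptomatic bacteriuria, so treating the whole outcome as unknown gives an upper limit.

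A reader might infer four stronger things that the documents do not support:

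- **That the satisfaction comparison must understate a UTI-related difference.** It need not if late-UTI patients rate much worse than early ones. Section IV.e also expects possible irritation from the sleeve, which could affect ratings independently of UTI.
- **That the primary result is likely to be overturned.** The limits above are logical extremes and no SAE rate is given.
- **That discontinuation after a UTI loses primary outcomes.** Such a patient already has her event if counting is cumulative, which the section IV.a window favours.
- **That length of stay, readmission, antibiotic use or cost will be biased.** These can come from charts. They are at risk only if extraction stops at discontinuation, which the plan leaves open.

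**Conclusion.** The point holds as a gap in outcome collection. Followed as written, the plan loses satisfaction responses according to the primary outcome, and the expected loss is twice as large in the control arm at the planned rates. With 25% to 75% of UTIs established before Visit 4 (assumption), 10 vs 5 to 30 vs 15 records are missing, and the UTI gap among responders falls to between 17.5 and 8.4 points. The comparison no longer reflects the randomised groups, and the documents do not allow the direction or size of the bias to be stated.

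For the primary outcome, a non-UTI SAE can leave late asymptomatic bacteriuria undetected. With 5% or 10% of each arm wholly unknown (assumption), the outer limits are 14 to 24 or 8 to 28 points. The effect on power is small. It should be fixed because these data cannot be recovered afterwards and the correction is cheap.

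**What to change.** Reconcile the UTI rule in IV.a, Visit 4 in IV.d and the SAE rule by stating that reaching the UTI endpoint or having an SAE does not end outcome data collection. Then:

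- For all randomised patients who are willing and able, collect the satisfaction questionnaire and chart data through the Visit 4 date.
- For those without a prior UTI, also collect the Visit 4 urine assessment already scheduled.
- Define the day-14 endpoint as any UTI from surgery through day 14 +/- 2, carry 24-hour cases forward as events, and align section VI with that.
- Report the number of unknown primary outcomes per arm, with a best/worst-case range.

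No change to the clinical handling of a UTI or SAE is proposed.

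This is a cheap improvement. Visit 4 is already the standard post-operative visit, so the cost is protocol wording and a little extra data collection. SAE patients without a UTI would have one urine dip that the plan already schedules. Section IV.e notes that an abnormal dip can lead to unnecessary treatment, and that risk should be acknowledged. Some patients will be unwilling or too ill, so a few values will still be missing.

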IV. Project Design and Procedures.

- a. Performance Measurement.** The primary outcome is UTI within 14 +/- 2 days post-surgery. A UTI is defined as an infection in any part of your urinary system which may include the kidneys, ureters, bladder, and urethra. Most infections involve the lower urinary tract (bladder and urethra), and are treatable with antibiotics. If a UTI spreads to the kidney, it can become a more serious complication. Women are at a greater risk of developing a UTI than men are. Pre-operative antibiotics will be collected to determine if this directly affects the outcome of a UTI. Visits to the ED for urinary pain, incontinence, or fever will also be followed for determination of UTI. Participants will provide a urine sample 0-24 hours before surgery. The sample will be tested with a rapid urine analysis (UA) test. This measure was chosen so that study UAs results are not to be confused with standard UAs conducted with samples collected after catheter placement. Participants will be followed up by research staff ~24 hours post-surgery for a second UA test. A third UA will be conducted at the patients' post-op check. At follow-up visits, participants will also

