Additionally, there is and will remain practice variations in catheter placement. While we hope to find a difference despite these differences, it is possible that the intervention may give a false impression of improvement simply by focusing attention on a protocol. While it is difficult to remove confounding from any study, randomization and analysis adjustments will be used to reduce as much as possible.

VI. Data Analysis Plan:

This study will assess a population of patients undergoing extended surgery requiring catheter placement to be performed by the Gynecologic Oncology service. De-identified patient data will be collected into OnCore and exported to SPSS for data analysis. Initial summary statistics will be performed to report the distribution of the data, including variable means, medians, proportions and missing data.

An intent-to-treat analysis will be conducted. All participants receiving treatment per protocol will be included in the final analysis. If there are any participants who are randomized but do not receive the intended treatment, we will document the reasons for their being withheld treatment.

For the primary outcome measure of UTI rate at each of the time points (24 hours and 14 +/- 2 days), we will perform a test of binomial proportions for testing the null hypothesis of no difference between the treatment arms. Because we are performing tests at two time points, we will adjust for the multiple comparisons using Bonferroni's method.

We will also explore the association between treatment arms and other covariates (symptomatic and demographics factors) using bivariate methods. The particular analysis method for testing the association between them will depend on the distribution of the covariates. For example, symptomatic presentation variables (fever, pelvic pain, sense of urgency or dysuria, and antibiotic use) are categorical, and their association with treatment arm will be evaluated with a chi-square statistic.

For demographic variables, Student's *t*-test (for continuous variables) and chi-square tests (for categorical variables) will be used to compare the two treatment arms. Variables found to be significant in these bivariate analyses will be included in multivariable analysis using logistic regression. Logistic regression models will be used to identify significant independent predictors associated with UTI

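### Antibiotic use is treated as cause, outcome, symptom and part of the UTI definition, so it can enter the UTI model as a covariate while the question about pre-operative antibiotics has no named analysis

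*Combined protocol and SAP*

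**What the plan says.** Antibiotic use has four roles.

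- **Possible cause.** Section IV.a: "Pre-operative antibiotics will be collected to determine if this directly affects the outcome of a UTI". Section IV.d, Visit 2, provides for the record: "Pre-operative antibiotics will also be recorded".
- **Secondary outcome.** Section IV.a lists "hospital length of stay, readmissions, antibiotic use at the time of surgery and post-surgery". Visit 4 in Section IV.d adds: "Data including hospital stay, readmission, and antibiotic use will be collected". Neither place gives a time window, an indication or a measure (any use, courses or days).
- **Symptom.** In Section IV.a participants will "be assessed for symptoms of UTI since surgery by assessment of" a list that includes "sense of urinary urgency, frequency or dysuria, fever, antibiotic use, and clinical and laboratory data suggesting infection". Section VI carries this forward: "symptomatic presentation variables (fever, pelvic pain, sense of urgency or dysuria, and antibiotic use) are categorical", to be compared between arms by chi-square.
- **Part of the primary endpoint.** Section IV.a: "Patients who are treated with antibiotics for UTI without laboratory data suggesting infection will be included in UTI group".

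Section VI also says that variables found significant in the bivariate comparisons of arms go into a multivariable logistic regression for UTI, with separate models at 24 hours and at 14 days. The chi-square is the only test named for antibiotic use. No analysis is named for it as a secondary outcome, and no model is said to contain pre-operative antibiotics.

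**The concern.** A variable that helps to define the outcome should not be a covariate in a model for that outcome. A woman treated for UTI without laboratory evidence is a UTI because she was treated. If antibiotic use enters the logistic model, it accounts for those UTIs itself, and the arm coefficient rests mainly on the others. The entry rule makes this worse: it admits antibiotic use when it differs by arm, which is what a working intervention should produce.

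Antibiotics given at surgery raise the opposite problem. The intervention is betadine on the catheter tip and a retained sleeve (Section IV.c), and nothing in the plan lets this change what is given at surgery. A difference there would reflect chance, or prescribing by staff who know the arm, since no masking is described. Such use belongs with the possible causes, where Section IV.a first puts it, yet it is listed as an outcome.

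At stake are the adjusted UTI result and the reading of the antibiotic outcome, not the unadjusted primary test.

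**Working it through.** **1. The plan's own figure.** Section IV.b: 40% v 20%, alpha 0.05, power 0.84, 100 per arm. Two-sided, with mean proportion 0.30:

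n = [1.960 × √(2 × 0.30 × 0.70) + 0.9945 × √(0.24 + 0.16)]² / 0.20² = (1.270 + 0.629)² / 0.04 = 90.2, so 91.

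Continuity correction: (90.2 / 4) × [1 + √(1 + 4 / (90.2 × 0.20))]² = 99.95, so 100. This matches. Without the correction, power at 100 per arm is 0.876. No figure is given for the antibiotic outcome.

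**2. Adjusting for antibiotic use.** Take the planned UTI counts per 100: 40 (standard) v 20 (aseptic). The unadjusted odds ratio is (20/80) / (40/60) = 0.375, with SE of its log √(1/40 + 1/60 + 1/20 + 1/80) = 0.323 and 95% CI 0.20 to 0.71.

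Suppose first that every recorded post-surgical course is for UTI. Every woman with a course is then a UTI by definition, so only women without one inform the arm coefficient:

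adjusted OR = (untreated UTIs, aseptic / 80) / (untreated UTIs, standard / 60).

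The documents give no split into treated and untreated UTIs, so these are assumptions (standard v aseptic):

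| Treated UTIs | Untreated UTIs | Adjusted OR (95% CI) | Chi-square p, antibiotic use by arm |
|---|---|---|---|
| 30 v 15 | 10 v 5 | 0.375 (0.12 to 1.15) | 0.011 |
| 30 v 10 | 10 v 10 | 0.75 (0.29 to 1.92) | 0.0004 |
| 20 v 15 | 20 v 5 | 0.19 (0.07 to 0.53) | 0.35 |

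- Row 1: with the same treated share in both arms (75%), the odds ratio is unchanged but the interval now includes 1.
- Row 2: if the protocol mainly prevents treated infections, the odds ratio moves toward 1.
- Row 3: the opposite pattern moves it away from 1, but antibiotic use then barely differs by arm and would not be selected.

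The entry rule thus favours row 2. Row 2 passes both the 0.05 in Section IV.b and the 0.005 in Section VI; row 1 passes only 0.05. If women without UTI also receive courses for other reasons, the shift is smaller. Fitting UTI on arm and antibiotic use to the expected counts of row 2 gives OR 0.50 with 10% such use and 0.45 with 20% (entry p = 0.004 and 0.017).

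**3. Pooling the two periods.** If antibiotics at surgery (share q, equal in both arms and independent) were merged with post-surgical use p, any use would be q + (1 − q)p. Assume p = 40% v 20%, borrowed from the UTI rates. Power is two-sided 0.05, uncorrected, 100 per arm:

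| q | Any use | Power |
|---|---|---|
| 0% | 40% v 20% | 0.88 |
| 25% | 55% v 40% | 0.57 |
| 50% | 70% v 60% | 0.32 |
| 75% | 85% v 80% | 0.15 |
| 90% | 94% v 92% | 0.08 |

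With p = 20% v 10%, power is 0.51 unpooled, 0.11 at q = 50% and 0.04 at q = 90%.

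**The case against.** **Pooling.** A reader might infer that the planned comparison is diluted by antibiotics given at surgery. The documents do not support that. Section IV.a names two periods, limits the symptom item to the time since surgery, and Section IV.d records pre-operative antibiotics separately at Visit 2. The Section VI chi-square can be read as post-surgical use only. This stands: the table in step 3 applies only if someone pools. What remains is that no text rules pooling out.

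**The aim.** A reader might also infer that the trial cannot answer its antibiotic-reduction aim. Section I presents less antibiotic use as an expected consequence of fewer UTIs; its hypothesis is UTI incidence. Post-surgical use could be compared from the data to be collected.

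**Cost.** Nor is the cost comparison diluted. Antibiotic cost at surgery adds to each patient's total and, if equal in expectation, cancels in the difference of means. It can add variance only.

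**The entry rule.** The sentence that admits significant variables stands in the paragraph on demographic variables, so it might be meant for those alone. It follows directly on the symptom tests, however, and refers to the bivariate analyses without limiting them. Section VI also speaks of predictors for each treatment arm. If models are fitted within arms there is no arm effect to bias, but antibiotic use would then appear as a predictor of an outcome it helps to define.

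**The covariate list.** Absence of pre-operative antibiotics from the demographics in Section IV.c does not show that they are excluded from modelling, since the confounders named in Section IV.a are absent there too. It remains true that no analysis of them is named.

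**Conclusion.** The concern holds as a conflict of roles with two consequences. First, as Section VI can be read, antibiotic use may be adjusted for in the UTI model although treatment for UTI is part of the UTI definition. On the assumed splits, the odds ratio of 0.375 either keeps its value with a much wider interval or moves toward no difference (0.45 to 0.75 in the row 2 case, depending on how much use is for other reasons). A shift toward no difference is not a mathematical necessity; it is the direction that the entry rule favours. Second, the question about pre-operative antibiotics has no named analysis, while use at surgery is listed as an outcome.

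The secondary outcome also lacks a window, an indication, a measure and its own test. The power loss from pooling is conditional on a step that the plan does not state. The treated shares, the use at surgery and the post-surgical rates are all assumptions. The unadjusted primary test and the 100 per arm are untouched.

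**What to change.** 1. In Section VI, remove antibiotic use from the variables that can enter the UTI model. It can still be recorded at the visits, because the endpoint definition needs it.
2. Take antibiotics at surgery out of the secondary outcomes and report them by arm. Pre-specify the recorded pre-operative antibiotics as a covariate in the supporting UTI model, whether or not they differ by arm. State that any given after unmasked randomisation are not strictly baseline.
3. Define the secondary outcome as antibiotic use started after surgery, excluding surgical prophylaxis, with a stated window, measure and test. Report use for all indications, and show use for UTI separately. Use for UTI alone would largely repeat the primary endpoint and depends on attribution by staff who may know the arm.
4. State that antibiotic data are still collected after a UTI. Section IV.a discontinues participants at that point, and they are the women most likely to receive a course.

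The cost is a few sentences in Sections IV.a and VI, plus start date and indication for each course on the case report form. The plan already takes outcomes from the chart but does not say that these two items are abstracted. No change in sample size is needed.
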